## 19.9 Handling of Missing Data

- CCI [REDACTED]
- CCI [REDACTED]
- To investigate the robustness of the analysis result for the primary endpoints, several sensitivity analyses will be performed. Details on these analyses will be provided in SAP.

## 20 Ethics and Protection of Human Subjects

### 20.1 Ethical Standard

As the Sponsor of this study, Biosense Webster has the overall responsibility for the conduct of the study, including assurance that the study meets the applicable European medical device regulation and the local government. For this study, MDR2017/745 will be applicable. The Sponsor will also maintain compliance with GCP (ICH E6 (R2), 9 November 2016), the European standard EN ISO 14155 (Clinical Investigation of Medical Devices for Human Subjects), the Declaration of Helsinki (Ethical Principles for Medical Research Involving Human Subjects, Fortaleza 2013), Sponsor general duties (21 CFR 812.40), selection of investigators (21 CFR 812.43), monitoring (21 CFR 812.46), supplemental applications (21 CFR 812.35 [a] and [b]), maintaining records (21 CFR 812.140 [b]), and submitting reports (21 CFR 812.150 [b]), and to local regulations where required.

- **General Duties:** Biosense Webster's general duties consist of submitting the clinical investigation application to appropriate regulatory agencies, assuring that sites have received EC approvals prior to shipping the devices, selecting investigators, ensuring proper clinical site monitoring, and ensuring subject informed consent is obtained.
- **Data Quality and Reporting:** Biosense Webster is responsible for providing quality data that satisfy federal regulations and informing proper authorities of serious unanticipated AEs and deviations from the CIP.
- **Selection of Investigators:** All potential investigational sites will undergo an evaluation to ensure that the site has the appropriate facilities and personnel to conduct the study in compliance with the clinical investigational plan. Based on outcome of evaluation process, Biosense Webster will select qualified investigators, ship devices only to participating investigators, obtain a signed Investigator's Agreement and provide the investigators with the information necessary to conduct the study.
- **Supplemental Applications:** As appropriate, Biosense Webster will submit changes in the Clinical Investigational Plan to the investigators to obtain all applicable re-approvals.
- **Maintaining Records:** Biosense Webster will maintain copies of correspondence, data, adverse device effects and other records related to the study. Biosense Webster will maintain records related to the signed Investigator Agreements.
- **Submitting Reports:** Biosense Webster will submit any required regulatory reports identified in this section of the regulation. This may include USADEs, withdrawal of EC approval, current investigators list, annual progress reports, recall information, final reports, and CIP deviations.

## 20.2 Informed Consent Process

### 20.2.1 Informed Consent Procedure and Documentation

Subjects informed consent must be obtained and documented according to the principles of informed consent in the latest version of the Declaration of Helsinki (Fortaleza, 2013), ISO 14155, and approved by the reviewing CA and EC.

Informed consent is mandatory and must be obtained from all subjects prior to their participation in the study.

Prior to screening or performing any study related procedures that are solely for the purpose of determining eligibility for this study, any potential benefits and risks of the study must be explained to the subject. Subjects will be informed about aspects of the study that are relevant to the subject's decision to participate. Subjects should be made aware that by signing the ICF, they are granting approval for study personnel to review their medical records and to collect/analyze personal medical information. Subjects should also be informed that study personnel will maintain confidentiality of the medical records at all times.

The ICF will be written in a native, non-technical, language that is understandable to the subject and is to be approved by the applicable EC prior to enrolling subjects. The subject or designee will be provided with ample time to read and understand the ICF and to consider participation in the study. Informed consent will be requested prior to enrollment and must be personally signed and dated by the subject, or subject's legal representative, prior to performance of any study related activity or procedure. If a subject is unable to read or write, informed consent shall be obtained through the aid of an independent witness who will be present throughout the process. The written ICF and any other

information shall be read aloud and explained to the prospective subject and, whenever possible, subject shall sign and date the ICF. The witness must also sign and date the ICF attesting that the information was accurately explained, and that informed consent was freely given. The point of enrollment corresponds with the time that subjects sign the informed consent. The subject will receive one copy of the fully signed ICF.

The investigator and/or designee must also clearly document the process of obtaining informed consent in the subject's source documents and maintain the investigational site's signed informed consent with the essential documents. The voluntary process of obtaining informed consent confirms the subject's willingness to participate in the study. It's the investigator's responsibility to ensure that the informed consent process is performed in accordance with ICH-GCP and, where applicable, local and federal regulations. Subjects should not be coerced, persuaded, or unduly influenced to participate or continue to participate in the trial. Subjects or his/her legal representative must be given ample time and opportunity to inquire about details of the trial and all questions about the trial should be answered to the satisfaction of the patient or the representative. Failure to provide written informed consent renders the subject ineligible for the study. If new information becomes available that can significantly affect a subject's future health and/or medical care, this information shall be provided to the subject(s) affected in written form. If relevant, all affected subjects shall be asked to confirm their continuing informed consent in writing by dating and signing the amended ICF.

### **20.3 Participant and Data Confidentiality**

During this clinical investigation, all representatives of the Sponsor will comply with all in-country privacy laws and regulations regarding contact with subjects, their medical record information, copying of information, and protection of the subject identities.

All information and data sent to Biosense Webster concerning subjects or their participation in this clinical investigation will be considered confidential. Only authorized Biosense Webster personnel or representatives (including contracted service providers, i.e. Core Lab, Clinical Research Associate, CRO, etc.), representatives of the FDA or CAs acting in their official capacities will have access to these confidential files upon request (including, but not limited to, laboratory test result reports, ECG reports, admissions/discharge summaries for hospital admission occurring during a patient's study participation and autopsy reports for deaths occurring during the clinical investigation). Some of the countries to which the study subjects and investigators personal data may be transferred may not offer as comprehensive a level of protection of personal data as within the European Union but Sponsor will take all reasonable steps to ensure a sufficient level of data protection. All data used in the analysis and reporting of this evaluation will exclude identifiable reference to the subject.

#### **20.3.1 Research Use of Stored Data**

- Intended Use: Data collected under this CIP may be used to study AF.
- Storage: Access to stored data will be limited. Data will be stored using codes assigned by the sponsor. Data will be kept in password-protected computers. Only investigators and the sponsor will have access to the data.

### **21 Source Documents and Access to Source Data/Documents**

Data entered on to the eCRFs will be taken from source documentation, such as hospital procedure reports, admission and discharge summaries, other hospital or investigator office/clinic documents, and system data (CARTO™, generator system). If unique study parameters are not documented on

standard hospital or office reports, a worksheet may be developed to record this information. The worksheet shall be signed by the PI or authorized designee and will serve as source document and as basis for monitoring the eCRFs. Electronic subject records will be considered as source documents on the condition that the hospital's database is a validated system. If this is not the case, electronic records should be printed and added to the subject's paper file. A print-out of a completed eCRF cannot be used as source documentation.

Investigators should maintain information in the subject's medical records, which corroborate data collected on the eCRFs. In order to comply with these regulatory requirements, at minimum, the following is a list of information that should be maintained.

- Medical history/physical condition of the study subject before involvement in the study sufficient to verify CIP selection criteria (if not already present).
- Dated and signed notes from the day of entry into the study including the study Sponsor (Biosense Webster), CIP number, clinical site, subject number assigned and a statement that consent to participate in the study was obtained.
- Dated and signed notes from each study visit with reference to the eCRFs for further information, if appropriate (for specific results of procedures and exams).
- Reports on AEs and their resolution, including supporting documents such as discharge summaries, EP lab reports, ECGs, lab results.
- Notes regarding CIP -required medication and prescription medications taken during the study (including start and stop dates).
- Notes on subject's condition upon completion of or withdrawal from the study.

Only authorized Biosense Webster personnel or representatives, authorized site personnel and government authorities acting in their official capacities, will have access to these confidential files.

## **22 Quality Assurance and Quality Control**

Quality Control (QC) procedures will be implemented beginning with the data entry system and ongoing QC checks will be run on the database. Any missing data or data anomalies will be communicated to the site(s) for clarification/resolution. Following written SOPs, monitors will verify that the clinical trial is conducted, and data are generated, documented, and reported in compliance with the CIP, GCP, and the applicable regulatory requirements. If noncompliance is identified, Sponsor is required by regulation to implement measures to secure compliance. The investigational site will provide direct access to all trial related sites, source data/documents, and reports for the purpose of monitoring and auditing by the sponsor, and inspection by local and CAs.

## **23 Data Handling and Record Keeping**

### **23.1 Data Collection and Management Responsibility**

The Sponsor will be responsible for all data management activities. These activities include development of an EDC system and utilizing a validated EDC system into which all study data will be entered. The Sponsor will be responsible for reviewing all data to ensure the overall integrity of the database.

### 23.1.1 Data Collection

eCRFs will be used to collect all subject data during this clinical investigation. eCRFs have been developed to capture the information outlined in this clinical investigation Plan. Modification to the eCRF will only be made if deemed necessary by the sponsor. Data on these eCRFs will be monitored (source verified) and the monitor will ask the site representative to correct, if necessary, to match the source documents. All changes made to the data will be tracked in the electronic audit trail. The investigator will be required to sign designated eCRFs as verification that they have been reviewed and the data entered are correct. Data from these eCRFs will be used to provide analysis of this clinical investigation.

### 23.1.2 Data Reporting

The investigator, or a designated individual, is responsible for ensuring that clinical investigation data are timely and properly recorded on each subject’s eCRF and related documents. The investigator, or a designated individual, is required to electronically sign the eCRF on the appropriate pages to verify that he/she has reviewed and attests to the correctness of the recorded data. Completed eCRF will be reviewed and monitored by the sponsor personnel, or an appropriately qualified and trained designee, throughout the clinical investigation. To this end, the Investigator and institution must permit inspection of the trial files and subject eCRFs by such representatives and/or responsible government agencies. Investigators are required to prepare and submit accurate and timely reports on this study to the governing EC and Biosense Webster as described in Table 11.

**Table 11: Responsibilities for Preparing and Submitting Reports**

Type of Report	Prepared by Investigator For	Time of Notification
Subject withdrawal	Biosense Webster	Should report within 5 working days
Withdrawal of EC approval	Biosense Webster	Should report within 5 working days
Clinical Investigation I report	Biosense Webster, EC	Will prepare a final report for the clinical investigation as required per national regulations.
Informed consent not obtained from subject	Biosense Webster, EC	Should report within 5 working days

It is recommended that all eCRF data be entered by the designated site personnel as soon as possible. For AE reporting, refer to the Adverse Event Reporting Requirements and timelines noted within this clinical investigation plan.

### 23.1.3 Data Verification and Review

Biosense Webster will track the amount of missing data and contact sites as appropriate to instruct them on steps to minimize missing data and remain compliant with CIP required assessments. Missing or unclear data will be queried as necessary throughout the trial. Biosense Webster will request further documentation such as physician and/or cardiac EP lab procedure notes when complications or device malfunctions/complaints are observed and reported. Biosense Webster will be responsible for auditing the database and confirming the overall integrity of the data.

#### **23.1.4 Final Data Analysis**

All exported datasets for analyses will undergo a final data review before final database lock. Once all critical data are monitored and locked, the final analyses of clinical investigation data will be performed.

#### **23.2 Study Record Retention and Archiving**

Records and reports for the study will remain on file at the site for a minimum of 10 years or per country specific record retention requirements following notification by the sponsor that all investigations have been terminated or completed, or in the event that the device is subsequently placed on the market, at least 10 years after the last device has been placed on the market. This documentation must be accessible upon request by the CAs, the sponsor, or a designee. The sponsor must approve archiving, transfer, and destruction of the documentation, in writing, prior to the actual archiving, transfer, and destruction. The investigator must notify the sponsor, in writing, of transfer location, duration, and the procedure for accessing the study documentation.

If the investigator retires, relocates, or withdraws from assuming primary responsibility for keeping the study records, custody transfer per written notice must be submitted to the sponsor indicating the name and address of the person accepting primary responsibility. The EC must be notified in writing of the name and address of the new custodian. Record retention dates must be provided to all parties by the sponsor's corporation.

Each Member State shall require that this documentation is kept at the disposal of the competent authorities for the period referred to in the first section of the paragraph, in case the Sponsor, or its contact person or legal representative as referred to in Article 62 (2) (MDR [EU - 2020/561]) established within its territory, goes bankrupt or ceases its activity prior to the end of this period.

#### **24 Study Suspension or Termination**

This clinical investigation may be temporarily suspended or prematurely terminated at the discretion of the Sponsor. The Sponsor may also terminate a site prior to study completion if the Sponsor believes the site is no longer capable of participating (e.g., cannot fulfill subject enrollment or CIP compliance goals, site suspension by EC). If the CI is prematurely terminated or suspended, the PI will promptly inform the EC and will provide the reason(s) for the termination or suspension.

If suspension or premature termination occurs, the terminating party shall justify its decision in writing and promptly inform the other parties with whom they are in direct communication. The PI and sponsor shall keep each other informed of any communication received from either the EC or the CA.

If early termination of the study is required due to safety concerns, each site will undergo a monitoring visit to conclude any outstanding issues, collect all outstanding CRF information, verify device accountability, and discuss any other items relevant to the conclusion of the CI. Any enrolled subjects will continue to be followed per the CIP requirements.

If, for any reason, the sponsor suspends or prematurely terminates the study at an individual study site, the sponsor shall inform the responsible CA as appropriate and ensure that the EC is notified, either by the PI or by the sponsor. If the suspension or premature termination was in the interest of safety, the sponsor shall inform all other PIs.

Circumstances that may warrant termination or suspension include, but are not limited to:

- If suspicion of an unacceptable risk, including serious health threat, to subjects arises during the clinical investigation, or when so instructed by the EC or regulatory authorities, the sponsor shall suspend the clinical investigation while the risk is assessed. The sponsor shall terminate the clinical investigation if an unacceptable risk which cannot be controlled is confirmed.
- Instructions by the EC or regulatory authority to suspend or prematurely terminate participation in a clinical investigation at the investigation sites for which they are responsible.
- Demonstration of efficacy that would warrant stopping.
- Insufficient compliance to CIP requirements.
- Data that are not sufficiently complete and/or evaluable.
- Determination of futility.

The clinical investigation may resume once concerns about safety, CIP compliance, data quality is addressed and satisfy the sponsor, EC and regulatory agency.

The Sponsor must notify the CA in case of a temporary halt or early termination of the clinical investigation. This notification must be made within 15 days of the temporary halt or early termination, providing a justification for the event. In the event that the sponsor has temporarily halted or terminated early the investigation on safety grounds, the CA must be informed within 24 hours of the event.

## **25 Study Completion**

The study end shall be deemed to coincide with the last visit of the last subject or last 12-month assessment date (i.e., Holter end date). The sponsor will inform the responsible CA within 15 days of the study end in a participating country. In addition, each CA will be notified within 15 days of the global study end.

Within one year of the end of the clinical investigation, the full final clinical investigational report must be submitted to the CA. A clinical investigation ends with the last visit of the last subject unless another endpoint is specifically set out in the clinical investigation plan.

## **26 Data and Publication Policy**

Publications and/or presentation of clinical investigation results will be coordinated and governed between Biosense Webster, Inc., the clinical investigation author(s) and if applicable local law. Authorship will be determined prior to development of any manuscript. All information concerning the study, investigational medical device, sponsor operations, patent application, manufacturing processes, and basic scientific data supplied by the sponsor to the investigator and not previously published, are considered confidential and remain the sole property of the sponsor. As per ISO 14155:2020 paragraph 5.4. a description of this clinical investigation will be registered in publicly accessible database (<http://www.ClinicalTrials.gov>) and content will be updated throughout the study. Results will be entered at completion of the clinical investigation.

## **27 Document Filing**

A copy of all approved versions of the Clinical Investigation Plan will be kept, by the site, in the Investigator Site File and in the Sponsor Trial Master File.

76. Deshmukh, A., et al., *In-hospital complications associated with catheter ablation of atrial fibrillation in the United States between 2000 and 2010: analysis of 93 801 procedures*. Circulation, 2013. **128**(19): p. 2104-12.
77. Stewart, M.T., et al., *Intracardiac pulsed field ablation: Proof of feasibility in a chronic porcine model*. Heart Rhythm, 2019. **16**(5): p. 754-764.
78. Hindricks, G., et al., *2020 ESC Guidelines for the diagnosis and management of atrial fibrillation developed in collaboration with the European Association for Cardio-Thoracic Surgery (EACTS): The Task Force for the diagnosis and management of atrial fibrillation of the European Society of Cardiology (ESC) Developed with the special contribution of the European Heart Rhythm Association (EHRA) of the ESC*. Eur Heart J, 2021. **42**(5): p. 373-498.
79. Sugrue, A., et al., *Irreversible electroporation for catheter-based cardiac ablation: a systematic review of the preclinical experience*. J Interv Card Electrophysiol, 2019. **55**(3): p. 251-265.
80. Marijon, E., et al., *Real-time contact force sensing for pulmonary vein isolation in the setting of paroxysmal atrial fibrillation: procedural and 1-year results*. J Cardiovasc Electrophysiol, 2014. **25**(2): p. 130-7.
81. Cronin, E.M., et al., *2019 HRS/EHRA/APHS/LAHR expert consensus statement on catheter ablation of ventricular arrhythmias*. Heart Rhythm, 2020. **17**(1): p. e2-e154.

## 29 Appendix 1

Definitions on effectiveness terms are mentioned below.

Term	Definition
Recurrent AF/AT/AFL	Recurrent AF/AFL/AT is defined as AF/AFL/AT of at least 30 seconds' duration that is documented by an ECG or device recording system and occurs following catheter ablation. Recurrent AF/AFL/AT may occur within or following the post ablation blanking period. Recurrent AF/AFL/AT that occurs within the post-ablation blanking period is not considered a failure of AF ablation.
Early recurrence of AF/AFL/AT	Early recurrence of AF/AFL/AT is defined as a recurrence of atrial fibrillation within three months of ablation. Episodes of atrial tachycardia or atrial flutter should also be classified as a "recurrence." These are not counted toward the success rate if a blanking period is specified.
Recurrence of AF/AT/AFL	
Recurrence of AF/AFL/AT post-ablation is defined as a recurrence of atrial fibrillation more than 3 months following AF ablation. Episodes of atrial tachycardia or atrial flutter should also be classified as a "recurrence."
 
Electrocardiographical occurrences of new onset non left atrial arrhythmia's, if confirmed by entrainment maneuvers during electrophysiology testing, should not be considered an ablation failure or primary effectiveness endpoint. Examples are:
 
 
• CTI dependant AFL. Cavotricuspid isthmus-dependent atrial flutter is easily treated with cavotricuspid isthmus ablation and is not an iatrogenic arrhythmia following a left atrial ablation procedure for AF.
 
• Atrioventricular nodal reentry tachycardia (AVNRT)
 

Off AAD	
As assessed from the end of the 3-month blanking period (Day 91 or Day of the visit whatever comes last) to 12 months following the ablation procedure.
 
Class I and III antiarrhythmic drug therapy, same dose as before procedure is not considered as failure. Class I and III antiarrhythmic drug therapy, higher dose or newly prescribed after procedure is considered as failure.
 
Class I and III antiarrhythmic drug therapy prescribed for other arrhythmia's than AF/AT/AFL is not considered as failure

### 30 Appendix 2

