### **7.4.2 Secondary Hypothesized Endpoints**

#### **12-Month Effectiveness**

Freedom from documented (symptomatic and asymptomatic) atrial arrhythmia (AF, AT or AFL of unknown origin\*) episodes based on electrocardiographic data ( $\geq 30$  seconds on arrhythmia monitoring device) during the effectiveness evaluation period (day 91-day 365) on or off antiarrhythmic therapy. Acute procedural failure (i.e., failure to achieve entrance block with the study device in any of the clinically relevant targeted PVs) will also be deemed a 12-month effectiveness failure.

*\*AFL of unknown origin is defined as all AFL except those CTI dependent AFL as confirmed by 12-lead electrocardiogram (ECG) or entrainment maneuvers in an EP study.*

Further refer to Appendix 1 for definitions on effectiveness terms.

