7.4.3 Secondary Effectiveness Endpoint

The secondary effectiveness endpoint is 12-month effectiveness success, which is defined as freedom from documented (symptomatic and asymptomatic) atrial arrhythmia episodes including atrial fibrillation (AF), atrial tachycardia (AT), or atrial flutter (AFL, of unknown origin*). The AF/AT/AFL episodes will be assessed based on the electrocardiographic data (≥ 30 seconds on arrhythmia monitoring device) during the effectiveness evaluation period (91-365 days post the index procedure). Acute procedural failure (i.e., failure to achieve entrance block with the study device in any of the clinically relevant targeted PVs) will also be deemed a 12-month effectiveness failure. The secondary effectiveness success rate will be compared against a performance goal of 50%.

The hypotheses to be tested for this evaluation are:

$$H_0: P_{12m} \leq 0.50 \text{ vs. } H_A: P_{12m} > 0.50,$$

where P_{12m} denotes the proportion of subjects who are failure-free at 12 months follow-up.

**AFL of unknown origin is defined as all AFL except those CTI dependent AFL as confirmed by 12-lead electrocardiogram (ECG) or entrainment maneuvers in an EP study.*

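### Appendix 1, to which the tested 12-month endpoint refers, exempts different arrhythmias on a different confirmation rule from protocol section 7.4.2 and SAP 7.4.3

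*Protocol*

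**What the plan says.** **Endpoint text.** Protocol section 7.4.2 counts documented AF, AT, or AFL of unknown origin from day 91 to day 365 as a 12-month failure. The only carve-out is in its footnote, which defines AFL of unknown origin as "all AFL except those CTI dependent AFL as confirmed by 12-lead electrocardiogram (ECG) or entrainment maneuvers in an EP study". SAP 7.4.3 repeats that footnote and lists the events that count as "atrial arrhythmia episodes including atrial fibrillation (AF), atrial tachycardia (AT), or atrial flutter (AFL, of unknown origin". Neither text exempts any AT by chamber of origin.

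**Link.** Section 7.4.2 closes with "Further refer to Appendix 1 for definitions on effectiveness terms". The visible SAP text on this endpoint does not cite Appendix 1.

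**Appendix 1.** The row on recurrence after ablation first classes later AF, and episodes of AT or AFL, as recurrence. It then makes an exception for new-onset arrhythmias that are not left atrial: these, "if confirmed by entrainment maneuvers during electrophysiology testing, should not be considered an ablation failure or primary effectiveness endpoint". CTI-dependent flutter and AVNRT are given as examples. The row calls the outcome it describes the primary effectiveness endpoint.

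**Status of the endpoint.** It is tested at a one-sided 2.5% level against a 50% performance goal, after both primary endpoints succeed, using a Kaplan-Meier estimate in the PP set (protocol 19.1 and 19.8.3; SAP 7.4.3 and 7.10).

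**The concern.** A tested endpoint needs one rule for what counts as an event. Here the endpoint section brings in a second rule by cross-reference, and the two differ on which arrhythmias are exempt and on what evidence is needed. The same documented episode can then be a success or a failure depending on which page is used.

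The affected cases are foreseeable. Entrainment requires an EP study, and repeat procedures are at the investigator's discretion (protocol 13.4), so some typical flutter may be documented by ECG alone. Conversely, a repeat procedure is where a right atrial AT could be identified by entrainment. The study is single-arm and unmasked (SAP section 3). The Clinical Events Committee is described as adjudicating primary safety events, and no visible text gives it the classification of recurrences.

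The label adds to the doubt. The primary effectiveness endpoint in this study is acute isolation of the targeted veins, and recurrence is the secondary hypothesized endpoint. Appendix 1 has evidently not been aligned with the endpoint hierarchy.

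**Working it through.** The plan states no figure on this point, so the check compares texts. A short calculation then gives the scale.

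**Step 1. Put events from days 91 to 365 through both rules.**

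| Event | Section 7.4.2 and SAP 7.4.3 | Appendix 1 recurrence row |
|---|---|---|
| New CTI-dependent AFL confirmed by entrainment | Exempt | Exempt |
| CTI-dependent AFL confirmed on 12-lead ECG, no EP study | Exempt | Exception not met; AFL is a recurrence by default |
| New right atrial AT confirmed by entrainment | Failure, since all AT counts | Exempt, as new-onset and not left atrial |
| CTI-dependent AFL that is not new, confirmed by either method | Exempt | Outside the exception, which covers new onset only |
| AVNRT | Not AF, AT or AFL, so not an event | Exempt |

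Rows 1 and 5 agree. Row 2 is the confirmation conflict, and Appendix 1 is the stricter text. Row 3 is the scope conflict, and Appendix 1 is the more lenient text. Row 4 is a smaller mismatch from the same sentence. Row 2 or row 3 alone is enough to show that one event can receive two classifications.

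**Step 2. Scale.** Inputs: n = 135 evaluable subjects (protocol 19.2), goal 50%, two-sided 95% interval. Assumption: all 135 are analysed and none is censored.

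- Shift from k reclassified subjects = 100 × k/135 percentage points. For k = 1 this is 0.74, for k = 3 it is 2.22, and for k = 5 it is 3.70. These values of k are illustrative.
- Plain interval (Greenwood variance without censoring): lower bound = p − 1.96 × √(p(1 − p)/135). At 79/135, p = 0.585 and the bound is 0.502, so the goal is met. At 78/135, p = 0.578 and the bound is 0.494, so it is missed.
- The exact interval, and the log-log form of the Kaplan-Meier interval, first clear 50% at 80/135 = 59.3%. The exact test then has an attained one-sided alpha of 0.0192.
- If 108 to 128 subjects were analysed (assumed range), the exact boundary would run from 65/108 = 60.2% to 76/128 = 59.4%, and one subject would be worth 0.93 to 0.78 points.

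The boundary is thus about 59% to 60% under any of these choices.

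**The case against.** **Appendix 1 is only a glossary.** It also has an off-drug failure row, although the tested endpoint applies on or off antiarrhythmic therapy. The flutter definition in 7.4.2 is repeated consistently elsewhere in the protocol and in the SAP. This is a good argument for letting the endpoint text govern, and the fix follows it. It does not remove the conflict, because 7.4.2 itself directs the reader to Appendix 1 and no visible sentence gives precedence. Redacted SAP text might do so.

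**Appendix 1 never says that entrainment is the only route.** True. But the row's default is that AFL is a recurrence, and its exception is conditioned on entrainment, so ECG-only flutter falls under the default.

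**The scope conflict is narrow.** This stands. CTI-dependent flutter is already exempt under 7.4.2 if confirmed, and AVNRT was never an event. What remains is essentially new-onset non-left-atrial AT proven by entrainment.

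**Stronger readings that the documents do not support.**

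- A reader might infer a third contradiction on duration. Appendix 1 speaks of at least 30 seconds' "duration that is documented by an ECG or device recording system and occurs following catheter ablation", while 7.4.2 has 30 "seconds on arrhythmia monitoring device", so AF on a short resting ECG might seem to count under one text and never under the other. The threshold is 30 seconds in both places, and 7.4.2 nowhere frees a 12-lead ECG from it. The idea that such an ECG could never count needs a tracing length that the documents do not give. The 3-month window (days 76 to 104) also straddles the end of blanking at day 90, and an ECG up to that day is no failure under either text. A 24-hour Holter is used at the 3-, 6- and 12-month visits as well.
- A reader might infer that Appendix 1 generally favours the device, or that events will be classified to suit the result. Only the AT case favours the device; the entrainment condition works against it. Independent core laboratories read the tracings, and nothing visible shows selective classification.

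**Conclusion.** The point holds for confirmation and scope. Section 7.4.2 with SAP 7.4.3, and the Appendix 1 row to which 7.4.2 leads, disagree on ECG-confirmed typical flutter and on entrainment-confirmed non-left-atrial AT. The two differences pull in opposite directions, so the net bias cannot be signed. The primary-endpoint label in Appendix 1 is also wrong.

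The likely effect on the result is small. The scale figures assume 135 analysed subjects and no censoring, whereas the test uses the PP set, Kaplan-Meier estimation and censoring for certain commercial RF use. The visible text does not specify the type of confidence interval. The conclusion is at risk only near the boundary, and the number of affected subjects cannot be estimated from the documents. The case for acting is that the ambiguity sits in the event definition of an alpha-controlled endpoint and costs almost nothing to remove.

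**What to change.** 1. State in section 7.4.2 that its definition, with SAP 7.4.3, governs the 12-month endpoint.
2. Rewrite the Appendix 1 recurrence row to match: among AF, AT and AFL the only exempt arrhythmia is CTI-dependent AFL, confirmed by 12-lead ECG or entrainment; all AT counts; the new-onset condition goes.
3. Correct the label in that row to secondary effectiveness endpoint.
4. Do this before 12-month events are classified.

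Two additions are optional: one sentence saying whether the 30-second threshold applies to 12-lead ECGs, and one sensitivity analysis that counts AFL exempted on ECG alone as failure.

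The cost is a few lines of wording, plus one extra run if the sensitivity analysis is adopted. No new data collection is needed.
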